## **15 Serum concentrations of Interleukin 1 receptor antagonist (IL-1Ra)/anakinra**

The serum concentration of endogenous IL-1Ra/anakinra at baseline, Day 8, Day 15, Day 28 and Week 12 for the first flare and subsequent flare will be presented by descriptive statistics.

## **16 Safety analyses**

The safety population is based on actual treatment during first flare and there is a risk that patients' treatment at new flares differs from the first flare. Therefore the number of patients and the actual treatment for each of the subsequent flare will be tabulated versus the number of patients in the treatment groups assigned for the safety population.

### **16.1 Drug exposure**

Treatment exposure, calculated as total amount anakinra/triamcinolone given per flare in mg will be presented for each flare and for the whole study by descriptive statistics (see Section 18.23).

### **16.2 Adverse events**

All analyses of AEs will be based on the safety population. No hypothesis testing will be performed. AEs will be coded using MedDRA Version 19.1. Percentages will be based on the number of patients in the safety population for the specific treatment group.

Since a subsequent flare can occur before the AE reporting period for the current flare has ended, the actual length of the AE reporting period can differ between patients. The actual length of the AE and the SAE reporting period will be presented by descriptive statistics for each flare and for the whole study.

A TEAE is defined as an AE with a start date/time after the first administration of IMP and not after the last day of the AE reporting period for each flare. AEs with unknown start date/time will be assumed to be treatment emergent unless the end date/time is known to be before the first administration of IMP. Pre-treatment AEs will be identified as AEs with a start date/time before the first administration of IMP (see Section 18.24).

The number and percentage of patients with at least one TEAE, at least one severe TEAE, at least one serious TEAE, including death, at least one non-serious TEAE, any related TEAE, any fatal TEAE, any TEAE leading to drug withdrawn and any TEAE leading to study withdrawal will be summarized.

The number and percentage of patients with at least one TEAE will be summarized in frequency tables by SOC and PT. This table will be repeated by BMI ( $<30.0$ ,  $\geq 30.0$  kg/m^2), sex, age ( $<65$ ,  $\geq 65$  years), race, and by ethnic origin for each flare and overall.

The number and percentage of patients with at least one TEAE will be summarized in frequency tables separately by day of onset: Day 1 to 5, Day 6 to 15 and after Day 15 by SOC and PT for each flare and overall.

The number and percentage of patients with at least one TEAE will be summarized in frequency tables by PT in descending order of frequency in the combined anakinra group for each flare and overall.

The number and percentage of patients with at least one TEAE will be summarized in frequency tables by PT, classified by maximum severity, in descending order of frequency in the combined anakinra group for each flare and overall.

The number and percentage of patients with at least one TEAE will be summarized in frequency tables by PT, classified by relationship in descending order of frequency in the combined anakinra group for each flare and overall.

The number and percentage of patients with non-serious TEAE will be presented by SOC and PT in descending order of frequency in the combined anakinra group for each flare and overall.

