7.5.6.1.2 Adverse event reporting period

The period for recording all adverse events, including SAEs, on the eCRF begins upon receiving the first dose of IMP and ends at visit E, 28 days after the first dose of IMP. SAEs will also be collected from signing of the ICF until the Week 12 visit (Visit 5). Furthermore, any SAE should be reported irrespective of the time of occurrence if a causal relationship between the event and the IMP(s) is suspected, Figure 2.

If the patient is treated with IMP for a subsequent flare, the adverse event (including SAE) reporting period starts again when the first dose is administered.

Refer to section 7.5.6.1.4 for information how unresolved adverse events and SAEs should be followed up.

Figure 2 AE reporting

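### Overall adverse-event percentages depend on how often each arm is re-treated, because non-serious events are recorded only for up to 28 days after the first dose for each treated flare

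*SAP*

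**What the plan says.** Protocol 7.5.6.1.2 sets the period for recording all adverse events: it "begins upon receiving the first dose of IMP and ends at visit E, 28 days after the first dose of IMP". When a later flare is treated with study drug, "the adverse event (including SAE) reporting period starts again when the first dose is administered". Serious events are followed longer, to the Week 12 visit, and after that if a causal link is suspected. Outside the periods, the Week 12 visit and the retention calls take no new non-serious events (Protocol 7.5.1.9 and 7.5.1.10). Follow-up runs to 52 weeks after the last randomization, with a maximum of 104 weeks per patient (Protocol 7.2.1).

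SAP 16.2 counts an event as treatment-emergent only if it starts after the first dose and "not after the last day of the AE reporting period for each flare". Several tables of patients with at least one such event are given "in descending order of frequency in the combined anakinra group for each flare and overall". The denominator rule is: "Percentages will be based on the number of patients in the safety population for the specific treatment group".

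On unequal observation, SAP 16.2 says that "the actual length of the AE reporting period can differ between patients". The reason it gives is that a new flare may occur before the current period has ended. Its response is to describe the period lengths, per flare and for the whole study. Neither document plans an event rate per unit of reporting time or per treated flare. For efficacy at later flares, by contrast, SAP 14.3.1.10 bases the percentages of responders, onset and resolution on patients who experienced that number of flares.

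**The concern.** A patient with one treated flare has one period in which a non-serious event can be recorded; a patient with four has up to four. The number of periods is decided after randomization and may depend on treatment. The overall percentage of patients with at least one event therefore mixes two things: the risk attached to a course of treatment, and how many courses were given and observed. If one arm is re-treated more often, its overall percentage rises with no difference in tolerability per course.

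The effect can also run the other way. A patient withdrawn from treatment for a safety concern judged related to study drug is not re-treated and leaves the study after Visit E (Protocol 7.3.3.1 and 7.3.3.2). An arm that is harder to tolerate can thus lose later observation periods.

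This matters because Protocol 7.2.1 gives safety and immunogenicity as the primary aim of the extension, and Protocol 5.1.4.2 and 5.3 raise the possibility that repeated short courses increase antibody formation, allergic reactions and injection-site reactions. A crude whole-study percentage cannot separate a higher risk per course from a larger number of courses.

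**Working it through.** The documents state no adverse-event risk and no re-flare rate, so there is no planned figure to reproduce. From the documents come the 28-day period, its restart at each treated flare, the 14-day minimum before re-treatment (exclusion criterion 21), the follow-up of 52 to 104 weeks and the safety-arm denominator. The risk per treated flare q and the mean number of re-treatments m are assumptions.

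**Share of follow-up observed.** Over 52 weeks (364 days), one treated flare covers 28/364 = 8%. Four cover at most 112/364 = 31%, and less if a period is cut short.

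**Overall percentage at equal risk per flare.** With one first flare plus a Poisson number of re-treatments, and events independent across flares, P(at least one event) = 1 − (1 − q)·exp(−mq).

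| q | m compared | Overall percentages |
|---|---|---|
| 35% | 1.5 v 1.0 | 61.5% v 54.2% |
| 35% | 2.0 v 1.0 | 67.7% v 54.2% |
| 20% | 1.5 v 1.0 | 40.7% v 34.5% |
| any | equal | no difference |

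**Clustering within patients.** Let q vary between patients as a beta distribution with mean 35% and average the same formula over it. For m = 1.5 v 1.0, an intra-patient correlation of 0.3 gives 53.0% v 48.1%, so the gap falls from 7.3 to 4.9 points. At 0.5 it is about 3.4 points.

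**Simulation with cut-off periods.** Settings: 28-day periods ended by the next treated flare, a minimum gap of 14 days, follow-up uniform over 52 to 104 weeks, constant hazard within a period and a 20% risk per full period.

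| Re-flares per year | Overall % of patients | Events per 100 periods of 28 reporting days | Events per 100 treated flares |
|---|---|---|---|
| 0.5 | 30.7 | 22.4 | 22.3 |
| 1.0 | 39.2 | 22.2 | 22.0 |
| 1.5 | 46.8 | 22.2 | 21.9 |
| 2.0 | 53.0 | 22.3 | 21.9 |

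The crude percentage climbs while both event rates stay flat. The first-flare percentage hardly moves: 19.9% at 0.5 re-flares per year and 19.7% at 1.5.

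**Later-flare tables.** Taken literally, the denominator rule applies to flare 2 as well. The share re-treated is 1 − exp(−m). At q = 20%, m = 0.5 gives 0.393 × 20% = 7.9% and m = 1.5 gives 0.777 × 20% = 15.5%, although the risk among those treated is 20% in both.

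**A rate that does not help.** Dividing patients with an event by all reporting time reverses the bias. At q = 35% and m = 1.5 v 1.0, mean reporting time is 2.5 × 28 = 70 v 2.0 × 28 = 56 days. This gives 61.5/70 = 0.88 v 54.2/56 = 0.97 patients per 100 patient-days, and 61.5/2.5 = 24.6 v 54.2/2.0 = 27.1 per 100 treated flares. The arm re-treated more often now looks safer at equal risk.

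**The case against.** The main comparison of safety is protected. The secondary objectives (Protocol 6.2, SAP 3.2) word safety as compared to triamcinolone only for the first flare. First-flare tables are planned (Protocol 9.3.6.1, SAP 16.2), and there each patient has one period. No tests on adverse events are planned, and the trial is an exploratory phase 2 study. This stands. A reader might infer that the trial's safety comparison as a whole is unsound; the documents do not support that.

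Much of the context is also planned: tables by flare, lengths of the reporting periods, number of treated flares (SAP 10) and exposure in mg (SAP 16.1). A reader could see an imbalance in re-treatment, but could not correct an individual system-organ-class or preferred-term percentage for it.

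The overall percentage is a legitimate description of cumulative recorded burden under a repeat-treatment strategy, and a rate per treated flare conditions on a post-randomization event. Both points are fair. They argue for showing the two side by side and labelling them, not for dropping the percentage.

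Finally, the SAP sentence on differing lengths might be read as acknowledging the whole problem. It concerns only periods shortened by an early re-flare. The larger driver, the number of periods per patient, is not mentioned.

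**Conclusion.** The point holds conditionally. The overall percentages respond to re-treatment frequency as well as to risk per course, and no planned measure separates the two. In the illustrations the spurious gap is 7.3 points (61.5% v 54.2%) for a 50% difference in mean re-treatments at an assumed 35% risk, and roughly 3 to 5 points with strong clustering. It is zero if re-treatment is equal.

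A reader might go further and infer that one arm will re-flare more, or that the tables will be biased against a particular arm. Nothing in the documents supports that: they give no re-flare or event rates by arm, so neither direction nor size can be stated. The distortion of the tables for flare 2 onward depends on applying the SAP 16.2 denominator rule as written. First-flare tables remain a sound basis for comparing the arms. This is a worthwhile improvement to the whole-study and extension presentations, not a flaw in the first-flare safety comparison.

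**What to change.** Amend SAP 16.2, and the tables that follow it, as follows:

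- In the overall and extension tables, add by arm the number of events per 100 patient-days of adverse-event reporting period and per treated flare, beside the crude percentages.
- If patients with at least one event are also shown as a rate, count reporting time only up to the first event.
- In per-flare tables from flare 2 onward, use patients treated with study drug for that flare as the denominator, in line with the approach in SAP 14.3.1.10.
- State that safety is compared between arms on the first-flare tables and these event rates, and that the overall percentages describe cumulative burden.

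The cost is SAP wording and extra columns. The data are already collected, and the period lengths and flare counts are already to be tabulated. The time-based rate assumes a roughly constant hazard within the period, which is one reason to show the rate per treated flare as well.

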5.2 Study rationale

The main aim of this study is to evaluate the efficacy and safety of anakinra in patients for whom NSAIDs and colchicine are either contraindicated or not appropriate, not tolerated or do not provide an adequate response, and to select the appropriate dose in order to reduce the pain and inflammation of a gouty arthritis flare. The study will also evaluate the safety and immunogenicity of anakinra when treating subsequent flares during a 1-2 years study extension.

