9.3.6.1 Adverse events

All adverse events will be coded using the latest version of Medical Dictionary for Regulatory Activities (MedDRA).

The number and percent of patients with at least one adverse event recorded at each level of summarization will be summarized in frequency tables by treatment, system organ class, preferred term, relation to investigational product and maximum severity. Percentages will be based on the number of patients in the safety population for the specific treatment group.

The number and percent of patients with at least one SAE, including death, at least one non-SAE, and adverse events leading to investigational product discontinuation will also be tabulated by system organ class and preferred term. Separate presentations will be made for the double-blind period (first flare) and the extension period.

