### **16.2.1 Serious adverse events**

The number and percentage of patients with serious TEAE will be presented by SOC and PT in descending order of frequency in the anakinra group for each flare and overall. The narratives will be presented in listings.

The number and percentage of patients with at least one pre-treatment SAE will be summarized in frequency tables by SOC and PT.

The number and percentage of patients with at least one SAE will be summarized in frequency tables separately by day of onset: Day 1 to Day 28 and after Day 28 for each flare and overall.

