### **16.2.2 Adverse events leading to withdrawal**

The number and percentage of patients with TEAEs leading to study withdrawal will be presented by SOC and PT, in descending order of frequency in the anakinra group for each flare and overall.

The number and percentage of patients with TEAEs leading to drug withdrawal will be presented by SOC and PT, in descending order of frequency in the anakinra group for each flare and overall.

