## 18.24 Adverse event start/stop day

The start day of an AE will be linked to the specific flare, and is defined as:

*Start date of adverse event – Date for 1st IMP injection for latest flare + 1*

where the date for 1st IMP injection for latest flare is based on the latest flare prior to start of the specific AE.

The stop day of an AE is defined as:

*Stop date of the adverse event – Date for the 1st IMP injection for the latest flare + 1*

where the date for the 1st IMP injection for the latest flare is based on the latest flare prior to the start of the specific AE.

For AEs starting within 72 hours after the 1st IMP administration for the latest flare, the start hour will also be calculated and is defined as:

*Start date/time hour of adverse event – Date/time hour for 1st IMP injection for latest flare*

In addition for the subsequent flares the start and stop dates will also be calculated from the date for the 1st IMP injection for the 1st flare.

In case of incomplete or missing start date, the following rules will be applied:

- If the day is missing, and the month and year is the same as for the date for 1st IMP injection for the latest flare, the start date will be set to the date for 1st IMP injection for the specific flare. Otherwise the date will be set to YYYY-MM-01.
- If day and month are missing, and the year is the same as for the date for the 1st IMP injection for the first flare, the start date will be set to the date for 1st IMP injection for the specific flare. Otherwise the date will be set to YYYY-01-01.
- If day, month and year are missing, the start date will be set to the date for the 1st IMP injection for the first flare, i.e. baseline visit.

In case of incomplete or missing stop date for a resolved AE, the following rules will be applied:

- If the day is missing, the stop date will be set to the last day of the month, i.e. YYYY-MM-30/31 if this date becomes before the end of study date, otherwise the date will be set to end of study date.
- If day and month is missing, the stop day will be set to YYYY-12-31 if this date becomes before the end of study date, otherwise the date will be set to end of study date.
- If day, month and year is missing, the AE will be set to ongoing.

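### The SAP plans no single count of patients with an adverse event across all re-treated flares, although the protocol promises an extension-period presentation

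*SAP*

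**What the plan says.** **Protocol.** Section 9.3.6.1 plans adverse event tables by treatment, then tables of serious, non-serious and discontinuation events, and closes with: "Separate presentations will be made for the double-blind period (first flare) and the extension period". Section 5.2 says that the study will also "evaluate the safety and immunogenicity of anakinra when treating subsequent flares during a 1-2 years study extension". Section 7.2.1 describes the extension as mainly a study of safety and immunogenicity rather than efficacy.

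**SAP.** A typical sentence in Section 16.2 begins "The number and percentage of patients with at least one TEAE will be summarized in frequency tables by PT in descending order of frequency". Section 16.2 sets out most TEAE tables "by PT in descending order of frequency in the combined anakinra group for each flare and overall". Section 16.2.1 orders serious TEAEs "in descending order of frequency in the anakinra group for each flare and overall". Section 16.2.2 uses the same split for withdrawals ("The number and percentage of patients with TEAEs leading to drug withdrawal will be presented by SOC and PT"). The TEAE overview names no period. The sentence introducing the SOC/PT table names none either; the flare split there is attached to its subgroup repeats. No table is labelled extension period or pools flares 2 and later.

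On percentages, Section 16.2 says: "Percentages will be based on the number of patients in the safety population for the specific treatment group". Section 18.24 ties events to flares: "The start day of an AE will be linked to the specific flare". Section 5 lists one change to the adverse event analysis, the classification by anti-drug antibody (ADA) status, and does not mention the reporting periods.

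**The concern.** The protocol divides adverse event reporting into two periods, first flare and extension. The SAP divides it by flare number and adds a total over all flares. These divisions answer different questions, and the change is not declared.

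The missing quantity is simple: of the patients who were re-treated, how many had at least one event on re-treatment? It matters because safety in subsequent flares is a secondary objective (Protocol 6.2). Protocol 5.1.4.2 also states that repeated short courses had not been studied before, and names allergic reactions and ADA as possible consequences. An event type that occurs once or twice at each of several later flares would be spread over several small tables, with no line that brings the patients together.

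**Working it through.** **Plan's own figures.** The documents give no adverse event rate and no re-treatment rate, so there is no plan figure on this point to reproduce. Only the arm sizes are used, 106 anakinra and 53 triamcinolone (Protocol 9.1). These are not in dispute: with a 12 mm difference, SD 25 mm, two-sided 5%, 80% power and 2:1 allocation, the usual formula gives 52 + 104 = 156 against the stated 159.

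**Step 1. The periods side by side.**
- First flare: promised in the protocol, and met by the flare 1 tables where the SAP splits by flare.
- Extension as one period: promised in the protocol, absent from SAP 16.2 to 16.2.2.
- Single later flares and all flares together: in the SAP only.

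**Step 2. Can the extension count be recovered?** Let n1, n2, n3, … be the patients with an event in flare 1, 2, 3, …; O the patients with an event in any flare (the overall table); R the number re-treated; and D the distinct patients with an event in any flare from 2 on.
- From the per-flare tables: largest of (n2, n3, …) ≤ D ≤ smaller of (n2 + n3 + …, R). The sum exceeds D whenever one patient has events in two re-treated flares.
- From the overall table: O − n1 counts only patients whose events are all in flare 2 or later. Hence D = (O − n1) + B, where B is the number with events both in flare 1 and on re-treatment. B is not tabulated, so this gives only D ≥ O − n1.
- R can be obtained, because SAP Section 10 tabulates patients by number of treated flares. D in general cannot.

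**Step 3. Illustration, combined anakinra group, N = 106.** Assumptions that are not in the documents: 50% re-treated, 60% of those going on to each further flare, at most four flares, 20% of patients with an event per flare.
- Patients treated: flare 2, 53; flare 3, 0.6 × 53 ≈ 32; flare 4, 0.6 × 32 ≈ 19.
- Patients with an event: n1 = 21, n2 = 11, n3 = 6, n4 = 4.
- Bounds: 11 ≤ D ≤ 11 + 6 + 4 = 21, that is 21% to 40% of 53.
- Effect of the overall table: O could lie from 21 to 21 + 21 = 42. If O = 32, then O − n1 = 11 and the range does not narrow. If O = 36, it becomes 15 to 21. Only at O = 42 is D fixed, at 21.

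With 30% to 70% re-treated and 10% to 30% with an event per flare, the per-flare bounds run from 3 to 6 of 32 at one end to 22 to 43 of 74 at the other. The upper bound is about 1.9 to 2 times the lower throughout.

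**Step 4. The denominator.** Read literally, SAP 16.2 divides every adverse event count by the whole safety population of the arm. In the illustration, 11 patients at flare 2 would print as 11/106 = 10.4%, where 11/53 = 20.8% had an event among those treated. At the same 20% risk, the printed flare 2 figure would be 6/106 = 5.7% with 30% re-treated and 15/106 = 14.2% with 70% re-treated, so it would move with re-treatment and not with risk. SAP 14.3.1.10 already bases the subsequent-flare response, onset and resolution percentages on patients who had that flare.

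**The case against.** **Finer detail satisfies the promise.** The protocol does not say that later flares must be pooled, and the SAP shows them one by one. This has some force: the first-flare half is met, and every re-treated patient has a flare 2, so that table directly describes first re-exposure. It does not supply a patient count for the extension as a period, which Step 2 shows cannot in general be rebuilt.

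**Scope of the protocol sentence.** It ends the paragraph on serious, non-serious and discontinuation events and may cover only those tables. That is a fair reading, but the SAP lacks the extension presentation for those tables too. For the TEAE overview, the SAP is silent rather than contradictory.

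**Other outputs.** Deaths and serious events are listed with narratives, serious events are listed with the nearest ADA titers, events are tabulated by ADA status, and all data appear in patient listings. This stands: a signal would not rest on these tables alone, and a manual count is possible. The ADA tables cover the whole study, however, and do not isolate re-treatment.

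**Per-flare percentages compare better.** A cumulative proportion rises with the number of courses even at constant risk. This stands, and the fix allows for it.

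**Stronger readings that the documents do not support.**
- A reader might infer that patients with an event on re-treatment are not counted, or that the re-treatment question goes unanswered. The flare 2, flare 3 and later tables refute both.
- A reader might infer hidden risk from a figure such as 1 − (1 − 0.20)² = 36% over two courses against 20% per flare. That is only accumulation, at an assumed rate and with independence between flares.
- A reader might infer that flare 1 dominates the overall table. The documents give no re-treatment rate. If half of 159 patients had two to three re-treated flares each, there would be about 159 to 239 re-treated flares against 159 first flares.

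**Conclusion.** The gap is real and limited. The SAP omits the extension-period adverse event presentation that Protocol 9.3.6.1 promises, and Section 5 does not say so. One quantity is lost: the number of distinct patients with an event across all re-treated flares. Its size depends on rates that the documents do not give; under the assumptions in Step 3 the per-flare tables would locate it only to within a factor of about two.

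The literal denominator is a related weakness, since it would make percentages for flare 2 and later depend on how many patients were re-treated. Neither point touches the efficacy analysis or suggests that events go unrecorded, and the safety analysis is descriptive. The case for acting is that the missing table serves the main stated aim of the extension.

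**What to change.** In SAP 16.2 to 16.2.2:
- Add a presentation for the extension period (flares 2 and later) to the TEAE overview and to the SOC/PT, serious TEAE and withdrawal tables. Use as denominator the patients given IMP for at least one subsequent flare.
- Show events per treated flare alongside, because the cumulative proportion depends on how many flares each patient had treated.
- State that percentages for flare 2 and later use the patients treated for that flare.
- Keep the per-flare and overall tables.

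In SAP Section 5, record these denominators as a change, since Protocol 9.3.6.1 also bases percentages on the safety population of the arm. If the sponsor prefers the present layout, declare there that the extension-period presentation is dropped, and why.

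The cost is some SAP wording, one more run of existing table programs and extra output pages. No new data are needed, because events are already linked to flares. SAP 6.2 allows updates before the final database lock, when safety over all flares is analyzed.
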